7.2 Cardiac Changes

A patient who meets the below criteria based on the average of triplicate ECG readings will be withdrawn from the study:

• Change from baseline: sustained QTc > 60 msec

If a clinically significant finding is identified (including, but not limited to changes from baseline in QTcB or QTcF after study drug infusion), the investigator or qualified designee will determine if the patient can continue in the study and if any change in patient management is needed. This review of the ECG printed at the time of collection must be documented. Any new clinically relevant finding should be reported as an AE.

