9.4.2 Part 1 Primary Endpoints

9.4.2.1 Safety and Tolerability

All AEs will be coded using the most recent version of MedDRA. The incidence of AEs will be summarized by SOC and PT. Similar summaries will be produced for AEs by severity, SAEs, treatment related AEs, and AEs leading to discontinuation. AEs are collected from the first dose of study drug, thus all AEs are considered treatment emergent AEs.

The ECG results will be presented by visit, summarizing the continuous measurements based on the average of triplicate values, including the QT, QTc, QRS, RR, PR intervals, as well as change from baseline values, and clinically significant changes in heart rate and rhythm.

Reported values and change from baseline values of hematology, clinical chemistry and urinalysis (and the determinations relevant to the normal ranges and appropriate clinically significant or CTCAE toxicity gradings) will be summarized by laboratory test for each assessment day, using appropriate descriptive statistics.

Vital signs (systolic and diastolic blood pressure, pulse rate, respiratory rate, and oral temperature) will be summarized by assessment day showing absolute values, change from baseline values, and clinically significant changes (including orthostasis) using appropriate descriptive statistics.

Physical and neurological examinations will be summarized by assessment day showing shift from baseline.

Protocol TB006AD2102

Protocol Date and Version: 15 Oct 2021; v 3.0

The C-SSRS assessments will be presented in a by-subject listing.

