- Increase in QTcB from baseline ≥ 60 (msec).
- Increase in heart rate CFB% $\geq 30\%$ AND observed heart rate > 90 (bpm).

For categorical outliers:

- QTcB > 500 (msec).
- Increase in QTcB from baseline ≥ 30 (msec) and < 60 (msec).
- Increase in QTcB from baseline ≥ 60 (msec).
- Time-matched, placebo-adjusted QTcB CFB for all post-dose timepoints ≤ 24 hours.

The following figures are planned for presentation ECG parameter QTcB for both parts of study by treatment groups using the SAS:

- Mean observed values after study drug infusion on dosing days (by dose group)
- Mean observed values over time (excluding post-dose assessments on dosing days)
- Mean CFB after study drug infusion on dosing days (by dose group)

-
- Mean CFB over time (excluding post-dose assessments on dosing days)
 - Placebo-corrected mean CFB in QTcB with 90% CI whiskers across post-dose timepoints up to 24 hours (by dose group)

A time-matched analysis of change in QTcB will be graphically explored. The mean CFB in QTcB versus placebo will be plotted at the different timepoints \leq 24 hours post-dose, along with 90% 2-sided CI. The upper limit of the 90% CI should be below the 10 (msec) bound as provided by the International Conference on Harmonization (ICH) E14 guideline to be deemed as having no QTc prolongation effect. Due to the small number of subjects planned per cohort, subjects from the different cohorts will be pooled into active treatment and placebo. If any upper limits are observed above the 10 (msec) mark from the pooled plot, further exploration by cohort may be explored. The estimates and 90% CI will be obtained through an analysis of covariance (ANCOVA), using baseline QTcB as covariate and treatment (pooled active and placebo) as effect.

The following example SAS® code can be utilized and modified as needed:

```
Proc GLM Data = <Dataset>;
  By <Tmpt>;
  Class <TRT>;
  Model <CFB> = <TRT> <BaseVal> / solution;
  LSmeans <TRT> / diff cl Alpha = 0.1 pdiff;
  ods output LSMeanDiffCL = <estmt>;
  Run;
Quit;
```

Where <Dataset> is the input dataset, <Tmpt> is the timepoint, <TRT> is the treatment group, <BaseVal> is the baseline value and <estmt> is the output set containing the estimate and corresponding 90% CI.

The data for these presentations will be obtained from the following eCRFs:

- 12-Lead Electrocardiogram Details.
- Vital Signs (for heart rate).

Table 3 below gives the ECG measurements to be assessed.

Table 3. ECG Measurements

Measurement

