QT interval (msec)
QT, corrected with Bazett's formula (QTcB) interval (msec)
QRS interval (msec)
PR interval (msec)
Heart Rate (HR) (bpm)

The planned timings of these ECG are given in Appendix I: Schedule of Assessments and Procedures.

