13.2. PHYSICAL AND NEUROLOGICAL EXAMINATIONS

A listing of physical and neurological examination findings for both protocol parts will be presented separately using the SAS.

The information for the listing will be obtained from the following eCRFs:

- Physical and Neurological Examination
- Physical and Neurological Exam Abnormalities

It should be noted that weight will be presented and summarized alongside the vital signs (see Section 12.4 for details), and height will be presented alongside demographics and baseline characteristics (see Section 10.2 for details).

Body systems to assess include:

-
- Cardiovascular
 - Respiratory
 - Gastrointestinal
 - Neurological (Mental status, Motor and Sensory Skills, Hearing and Speech, Vision, Coordination, Balance)

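### The SAP's QTc outputs and its 10 msec statement rest on Bazett's correction alone, so a between-arm heart-rate difference would bias them; separately, the protocol's examination shift summary has become a listing without being declared

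*SAP*

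**What the plan says.** **QTc.** SAP Section 12.3, Table 3, lists QT, one corrected interval ("QT, corrected with Bazett's formula (QTcB) interval (msec"), QRS, PR and heart rate. QTcF and RR are absent. The marked-abnormality and categorical-outlier criteria, all the QTc figures and the placebo-corrected analysis are written for QTcB. On that analysis the SAP says "A time-matched analysis of change in QTcB will be graphically explored". It then gives a criterion for concluding that there is no prolongation: "The upper limit of the 90% CI should be below the 10 (msec) bound". The ANCOVA contains treatment (pooled active against placebo) and baseline QTcB, and nothing else. In the SAP, QTcF appears only in the abbreviation list.

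The protocol is broader. Section 7.2 asks the investigator to consider "changes from baseline in QTcB or QTcF after study drug infusion". Section 9.4.2.1 includes RR among the ECG intervals to be summarised and refers to QTc without naming a formula. Exclusion criterion 8 uses QTcB.

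**Examinations.** Protocol 9.4.2.1 states: "Physical and neurological examinations will be summarized by assessment day showing shift from baseline". SAP 13.2 states: "A listing of physical and neurological examination findings for both protocol parts will be presented separately using the SAS". SAP Section 8 declares one difference from the protocol, the dose-proportionality assessment.

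**The concern.** Bazett's formula divides QT by the square root of RR. If the true QT-RR relation is flatter than that, QTcB rises with heart rate when repolarisation has not changed, and falls when heart rate falls. With no rate term in the model and no second correction, a heart-rate difference between active and placebo after infusion enters the 10 msec comparison directly. A rise could suggest prolongation that is not there, and a fall could mask a real one. The outlier counts are not placebo-corrected, so they are affected by any rate change within a patient. Protocol 2.3.1 lists fever, chills and falls in blood pressure among the general risks of monoclonal antibodies, and these can move heart rate. It adds that they were not seen preclinically with TB006.

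Physical and neurological examinations are a primary safety endpoint in Part 1 and a secondary one in Part 2, for a drug aimed at the central nervous system. A listing gives the reader no tabulated comparison between arms.

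**Working it through.** **Part 1 of the check: size of the heart-rate effect.** The plan gives no figure to reproduce, so the effect is derived from the two definitions.

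- QTcB = QT / RR^(1/2) and QTcF = QT / RR^(1/3), with RR = 60/HR in seconds.
- Hence QTcB = QTcF × RR^(-1/6) = QTcF × (HR/60)^(1/6).
- Assumptions not in the documents: QTcF constant (no true effect) at 390-430 msec, and baseline heart rate 60-70 bpm.

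Worked case, QTcF 410 msec:

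- 65 bpm: 410 × (65/60)^(1/6) = 415.5 msec.
- 75 bpm: 410 × (75/60)^(1/6) = 425.5 msec, a shift of +10.0.
- 55 bpm: 410 × (55/60)^(1/6) = 404.1 msec, a shift of -11.4.

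Shift in QTcB (msec) over the assumed range:

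| QTcF | Baseline HR | +10 bpm | -10 bpm |
|---|---|---|---|
| 390 | 60 / 65 / 70 | +10.1 / +9.5 / +9.0 | -11.7 / -10.9 / -10.1 |
| 410 | 60 / 65 / 70 | +10.7 / +10.0 / +9.5 | -12.3 / -11.4 / -10.7 |
| 430 | 60 / 65 / 70 | +11.2 / +10.5 / +9.9 | -12.9 / -12.0 / -11.2 |

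A difference of +5 bpm gives +4.6 to +5.8 msec. A 10 msec artefact needs a between-arm rise of about 9-11 bpm or a fall of about 8-10 bpm.

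**Sensitivity to the true exponent.** If QT = 410 × RR^e, then QTcB = 410 × (HR/60)^(0.5 - e). For 65 to 75 bpm the shift is +12.1 msec at e = 0.30, +10.0 at 1/3, +7.2 at 0.38, +3.0 at 0.45 and 0 at 0.50. QTcF is not free of this problem. Its value is 410 × (HR/60)^(1/3 - e), so the same rise shifts it by 0 at e = 1/3, by 410 × (0.9896 - 0.9963) = -2.7 msec at 0.38, and by 410 × (0.9635 - 0.9867) = -9.5 msec at 0.50.

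**Part 2 of the check: the examination summary.** The two sentences quoted above cover the same assessments. The protocol calls for a summary of shifts by assessment day; the SAP plans a list of findings. No other SAP section tabulates them, and Section 8 is silent. The protocol text sits under the Part 1 primary endpoints, which covers 3 × 8 = 24 planned patients. For Part 2, Protocol 9.4.5 says that examination results will be presented as in Section 9.4.5, which is a reference to itself. Section 9.4.2.1 is presumably meant, which would bring in the 116 Part 2 patients, but the text does not say so.

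**The case against.** **On QTc.** The other side has several good points.

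- A reader might infer that the SAP departs from the protocol by using QTcB. The documents do not support that: Protocol 9.4.2.1 names no formula, eligibility uses QTcB, and the QTcF mention in Section 7.2 concerns the investigator's review of individual tracings.
- A reader might also infer that the 10 msec bound is a rule on which the drug could fail. The SAP calls the analysis a graphical exploration. The only follow-up it attaches to exceeding the bound is a possible look by cohort. Under Protocol 6.2.1 and 9.6, escalation depends on review by the Safety Review Committee, with QTc increases as one consideration.
- Heart rate and raw QT are tabulated as change from baseline, and individual heart-rate changes are flagged in SAP 12.3 and 12.4, so a rate effect would be visible. RR carries the same information as heart rate.
- The comparison is placebo-corrected, and nothing in the documents predicts a 10 bpm difference between arms.
- Precision matters as well. In Part 1 (18 against 6, 21 degrees of freedom) the 90% CI half-width is 1.72 × SD × sqrt(1/18 + 1/6), or 6.5 to 12.2 msec for an assumed SD of 8 to 15 msec.

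All of this stands, and it limits the weight of the point. What remains is that the SAP states a criterion for no prolongation, and the tabulated heart rate plays no part in it. With intervals that wide, a shift of a few msec can decide on which side of the bound the limit falls. The individual flags are also coarse: a rise from 65 to 75 bpm is 15% and 10 bpm, below both the 30% and the 15 bpm thresholds.

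**On examinations.** A reader might infer that a required table is lost for all 140 patients, or that abnormal findings reach no by-arm output. The first goes beyond the text, which is explicit for Part 1 only. The second overlooks Protocol 10.2.1, under which clinically significant abnormal safety assessments can become adverse events, and these are tabulated by treatment. That route is partial, because the same section excludes findings attributed to the underlying disease unless they are more severe than expected. In this population that could apply to many neurological findings.

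**Conclusion.** Both parts hold in a limited form.

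**QTc.** Reliance on QTcB alone is an avoidable weakness in an exploratory analysis, not a protocol violation. A between-arm heart-rate difference of about 10 bpm would by itself shift QTcB by roughly the whole 10 msec bound, given constant QTcF of 390-430 msec, baseline 60-70 bpm and a true exponent near 1/3. The shift shrinks as the true exponent approaches 0.50, and largely cancels where both arms change together. QTcF is the better basis only if the true exponent lies nearer 1/3 than 1/2. The documents do not settle that, which is why both corrections and the heart-rate change should be shown.

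**Examinations.** The loss of the shift summary is a direct and undeclared difference between protocol and SAP. It is explicit for about 24 Part 1 patients and presumably intended for Part 2.

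**What to change.** 1. In SAP Table 3 add QTcF and RR. Derive QTcF from QT and the RR or heart rate of the same ECG tracing. SAP 12.3 names the Vital Signs form as the heart-rate source, and a separately timed pulse should not be paired with an ECG QT. Protocol 8.2.3 has the central reader recording RR and heart rate in Part 1. In Part 2 the database keeps machine readings, so confirm that the machine heart rate is captured and use RR = 60/HR where RR is not.
2. Run the outlier tables, figures and time-matched ANCOVA on QTcF and base the 10 msec statement on it. Keep the QTcB versions as supportive. Show the between-arm heart-rate change at the same timepoints, and say how a disagreement between the two corrections will be read.
3. In SAP 13.2 restore the shift-from-baseline table by body system, visit and treatment group for both parts, with the neurological components shown separately. The scheduled post-baseline examinations are Days 36 and 104, plus early discontinuation where it occurs, so the table is short.
4. Correct the self-reference in Protocol 9.4.5.

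The cost is SAP wording, a protocol correction and a modest number of extra outputs. No new visits or procedures are needed.

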12.4. VITAL SIGNS

Listings will be presented on the following vital sign items separately for both protocol parts using the SAS:

- Quantitative results on all the tests listed in [Table 4](#).
- Potentially clinically significant results (Refer marked abnormalities listed under).

The following vital sign tables are planned to be presented, by treatment groups using the SAS:

- CFB with descriptive statistics on all the tests listed in [Table 4](#).
- Marked abnormalities including the following criteria:
 - Decrease in systolic blood pressure (SBP) of ≥ 25 (mmHg) versus baseline (orthostatic hypotension).
 - Decrease in diastolic blood pressure (DBP) of ≥ 15 (mmHg) versus baseline (orthostatic hypotension).
 - Increase/decrease in SBP of ≥ 20 (mmHg) versus baseline.
 - Increase/decrease in DBP of ≥ 10 (mmHg) versus baseline.
 - Increase/Decrease in Weight of $\geq 7\%$ versus baseline.
 - Increase/Decrease in Heart Rate by 15 bpm.

The data for these presentations will be obtained from the following eCRFs:

- Vital Signs.
- Physical Examination (for weight).

[Table 4](#) below gives the vital sign tests to be performed.

Table 4. Vital Sign Tests Performed

Test
Pulse (bpm)
Pulse oximetry, SPO ₂ (%)
Respiratory rate (brpm)
Supine DBP (mmHg)
Supine SBP (mmHg)
Temperature (°C)
Weight (kg)

The planned timings for the vital signs measurements are given in [Appendix I: Schedule of Assessments and Procedures](#).

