8.2.2 Vital Signs

- Oral temperature, pulse rate, respiratory rate, and blood pressure will be assessed as indicated in the SoA (Table 1 and Table 2).
- Blood pressure and pulse measurements will be assessed with a completely automated device. Manual techniques will be used only if an automated device is not available.
- Blood pressure and pulse measurements should be preceded by at least 5 minutes of rest with the patient in a quiet setting without distractions (eg, television, cell phones). Blood pressure measurements will be taken with the patient in the sitting position.
- Vital signs will be taken before blood collection for laboratory tests, if that is scheduled for the same time point.

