9.2. BASELINE DEFINITION

Baseline is defined as the last available value prior to the subject receiving first dose of study drug infusion (i.e., Day 1). If the potential Baseline ACR is on Day 1 (and time is not recorded), it is assumed that the ACR occurred before the start of first dose of study drug infusion.

CFB is calculated as:

$$\text{CFB} = \text{Observed value} - \text{Baseline Value}$$

Percentage change from Baseline (CFB%) is calculated as:

$$\text{CFB\%} = (\text{CFB} \div \text{Baseline Value}) \times 100$$

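### SAP 12.4 labels a fall in blood pressure from baseline as orthostatic hypotension and the readings as supine, but the protocol specifies sitting pressure only and no postural pair

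*SAP*

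**What the plan says.** Protocol 8.2.2 fixes one posture: "Blood pressure measurements will be taken with the patient in the sitting position". The vital-sign rows of protocol Tables 1 and 2 ask for readings before each infusion and at 2 and 6 hours after it ends on the five dosing days, and for one reading at each other scheduled visit. Neither schedule names a second posture.

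Protocol 9.4.2.1 nevertheless plans to summarise "clinically significant changes (including orthostasis") among the vital-sign results.

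SAP 12.4 sets two marked-abnormality rows, a systolic fall of 25 mmHg or more and a diastolic fall of 15 mmHg or more. Each is written as a change "versus baseline (orthostatic hypotension"). The same list has two further rows for a rise or fall of at least 20 mmHg systolic or 10 mmHg diastolic, with no postural label. SAP Table 4 names the tests as "Supine SBP (mmHg") and "Supine DBP (mmHg").

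On the reference value, SAP 9.2 states: "Baseline is defined as the last available value prior to the subject receiving first dose of study drug infusion". SAP section 8 lists only the dose-proportionality assessment as an addition to the protocol and says nothing about posture.

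**The concern.** Orthostatic hypotension is a fall in pressure on standing. To show it, a plan needs readings in two postures close together in time. The plan specifies one posture and compares it with an earlier value in that same posture. A row with this label would tell a reader of the study report that patients were checked for a postural fall and that some number had one. Neither statement would follow from the data.

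The error runs in two directions. A patient whose pressure is simply lower at a later visit is counted under a postural name. A patient with a true postural fall but a stable sitting pressure is not counted, so a low count could be taken as reassurance about something that was not measured.

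Vital signs belong to the safety endpoints, which are primary in Part 1 and secondary in Part 2 (SAP 6.3). The wording of these rows therefore reaches a main safety summary.

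**Working it through.** The plan gives no figure to reproduce, and the point does not rest on a calculation. The check sets the passages side by side.

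1. **Posture specified.** Protocol 8.2.2: sitting. No supine or standing reading is mentioned there.

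2. **Time points.** The schedules give 2 readings after the Day 1 infusion, 3 on each of Days 8, 15, 22 and 29, and 1 on each of Days 36, 64 and 104. That is 2 + 4 × 3 + 3 = 17 scheduled readings after the first infusion starts. None is described as a pair in two postures.

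3. **Reference value.** Under SAP 9.2 it is one value from before the first infusion. If the Day 1 pre-dose reading is taken, that is the baseline. The remaining Day 1 readings are then compared with a value from a few hours earlier. The Day 104 reading is compared with a value 104 − 1 = 103 days earlier, or 103 / 7 ≈ 14.7 weeks. At every interval the comparison is between two times.

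4. **What the rule detects.** It is met when (observed value − baseline value) ≤ −25 mmHg systolic or ≤ −15 mmHg diastolic. Both terms come from the same kind of reading. No term in the rule is a change of posture.

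5. **Overlap with the unlabelled rows.** Since 25 > 20 and 15 > 10, every fall that meets a labelled row also meets the corresponding unlabelled row. One reading would appear once as a plain change and once as a named condition, though the two rows differ only in threshold.

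6. **Posture named in the SAP.** SAP Table 4 says supine, against sitting in protocol 8.2.2. SAP section 8 declares no such departure. SAP Table 4 also lists pulse oximetry, which protocol 8.2.2 does not, so the table was not simply taken from that section.

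7. **Effect of correcting the label.** The thresholds, the baseline and the readings stay as they are. The same patients are flagged before and after, so the change in counts is zero. What changes is what the rows can be said to show.

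**The case against.** The best defence is that little harm follows. Each row states its own definition, so a careful reader sees that it counts a fall from baseline. Placebo is tabulated alongside, the tables carry no test, and wider changes are shown without the label. All of this stands and keeps the point minor. It does not make the label correct.

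Several stronger readings are tempting, and the documents do not support them.

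- *The condition is never assessed.* This is too strong. Orthostatic hypotension could be reported as an adverse event. What is missing is a postural vital-sign measurement.
- *Sitting is the right word for SAP Table 4.* This cannot be settled from the two documents. SAP 12.4 draws on the Vital Signs eCRF. The eCRF specification cited in SAP section 14 is dated 09 November 2021, after the protocol of 15 October 2021, and it was not available for this review. If sites recorded supine pressure, writing sitting would introduce an error.
- *A sizeable share of patients would be labelled falsely.* Neither document gives a standard deviation for change in blood pressure, and SAP 12.4 does not say whether the table counts patients ever flagged or patients flagged at each time point. Any percentage would rest on assumptions about both. It would describe how sensitive the thresholds are, and relabelling leaves them unchanged, so it would not measure the labelling error.
- *Dose escalation is compromised.* Protocol 6.2.1 has the Safety Review Committee weigh vital-sign changes among several variables. Nothing ties its decisions to this label.

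**Conclusion.** The point holds as an error of definition in a descriptive safety table. Followed as written, two rows of SAP 12.4 would report a postural condition that the specified measurements cannot show. The posture in SAP Table 4 conflicts with protocol 8.2.2. The orthostasis summary in protocol 9.4.2.1 has no data behind it in the plan, so the mismatch lies within the protocol as well as between the two documents.

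The size is small. Two row labels and two test names are affected. No count changes, the falls remain valid as decreases from baseline, and no efficacy result is touched. No numerical magnitude is offered, because none can be derived from the documents.

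The conclusion assumes that the eCRF collects no postural pairs beyond those in the protocol. If it does collect them, the rule in SAP 12.4 still does not use them, because it compares with baseline.

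**What to change.** - In SAP 12.4, remove the orthostatic hypotension label from both rows and title them as decreases in systolic and diastolic pressure from baseline. Keep the thresholds as written.
- Confirm from the Vital Signs eCRF which posture was recorded, then make SAP Table 4 and protocol 8.2.2 agree. If the recorded posture differs from the protocol, declare the departure in SAP section 8.
- State in SAP section 8 that the orthostasis summary planned in protocol 9.4.2.1 cannot be produced from the data specified. If postural pairs turn out to have been collected, define instead a rule that uses them.

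The cost is a few lines in the SAP or an addendum, the matching table shells, and one check of the eCRF. No new data or programming of thresholds is needed. Deleting the orthostasis text from the protocol would be more than a label change: it amends the protocol, and amendments go to the ethics committee under protocol 10.1.1. An entry in SAP section 8 avoids that and leaves the unmet commitment visible.

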10.2.1 Definition of AE

AE Definition

- An adverse event (AE) is any untoward medical occurrence in a patient or clinical study patient, temporally associated with the use of study drug, whether or not considered related to the study drug.
- NOTE: An AE can therefore be any unfavorable and unintended sign (including an abnormal laboratory finding), symptom, or disease (new or exacerbated) temporally associated with the use of study drug.

Events Meeting the AE Definition

- Any abnormal laboratory test results (hematology, clinical chemistry, or urinalysis) or
 other safety assessments (eg, ECG, radiological scans, vital signs measurements),
 including those that worsen from baseline, considered clinically significant in the
 medical and scientific judgment of the investigator (ie, not related to progression of
 underlying disease).
- Any new condition detected or diagnosed after study drug administration even though it may have been present before the start of the study.
- Signs, symptoms, or the clinical sequelae of a suspected drug-drug interaction.
- Signs, symptoms, or the clinical sequelae of a suspected overdose of either study drug
 or a concomitant medication. Overdose per se will not be reported as an AE/serious AE
 (SAE) unless it is an intentional overdose taken with possible suicidal/self-harming
 intent. Such overdoses should be reported regardless of sequela.

Events NOT Meeting the AE Definition

- Any clinically significant abnormal laboratory findings or other abnormal safety
 assessments that are associated with the underlying disease, unless judged by the
 investigator to be more severe than expected for the patient's condition.
- The disease/disorder being studied or expected progression, signs, or symptoms of the disease/disorder being studied, unless more severe than expected for the patient's condition.
- Medical or surgical procedure (eg, endoscopy, appendectomy): the condition that leads to the procedure is the AE.
- Situations in which an untoward medical occurrence did not occur (social and/or convenience admission to a hospital).

Protocol TB006AD2102

Protocol Date and Version: 15 Oct 2021; v 3.0

 Anticipated day-to-day fluctuations of pre-existing disease(s) or condition(s) present or detected at the start of the study that do not worsen.

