12.1. ADVERSE EVENTS

The following AE definitions are applicable to both protocol parts of this study:

- AE reporting period: Defined from start of first dose of study drug infusion on Day 1 up to and including End of Study.
- AE: Any untoward medical occurrence in a subject.
- Treatment-emergent AE (TEAE): Defined as any AE that started on or after first dose of study drug infusion within the studies' AE reporting period.
- SAE: Defined as any AE that is indicated as serious on the AEs Details eCRF, as per investigator's assessment.
- Related AE: Defined as any AE that is indicated as related to study drug on the AEs Details eCRF, as per investigator's assessment.
- AE leading to discontinuation: Defined as any AE that has an "other action taken" indicated as "withdrawn from study" on the AEs Details eCRF.

All AEs will be coded using the MedDRA version 22.1, Sep 2019. The following AE items will be listed separately for each protocol parts using the SAS:

- All AEs
- AEs leading to study discontinuation
- Serious AEs
- AEs leading to death (if applicable)

The following items are planned to be presented in summary tables showing event incidence and corresponding subject count, experiencing said AE/AE type using the SAS, by treatment groups using SAS:

- AE overview, including row items for frequency of subjects [n(%)] experiencing:
 - At least one AE
 - AEs by toxicity grade
 - Grade 1
 - Grade 2
 - Grade 3
 - Grade 4
 - Grade 5
 - Serious AEs

- Related AEs
- Non-related AEs
- AEs leading to study discontinuation
- AEs leading to death
- AEs by system organ class (SOC) and preferred term (PT)
- AEs by descending incidence of PT
- AEs by toxicity grade (Common Terminology Criteria for Adverse Events [CTCAE] grading)
- Related AEs by SOC and PT
- Related AEs by descending incidence of PT.
- Serious AEs
- AEs resulting in death
- AEs leading to study discontinuation

Only TEAEs will be used for summarization of all tables, but for listing all AEs will be counted. The TEAE status will be derived using the AE start and stop dates as per definition provided at the start of this section. For partial dates see [Section 9.4.1](#).

The data for these presentations will be obtained from the Adverse Events Details eCRF.

AE assignment to CTCAE toxicity grades is explained in [Table 2](#) below.

Table 2. CTCAE Grades

Grade	Grade Description	Grade Details

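### SAP 12.4 puts blood-pressure rises and falls on one line at 20/10 mmHg and refers every change to the Day 1 baseline, so modest falls after infusions 2 to 5 are hard to see

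*SAP*

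**What the plan says.** SAP 12.4 plans, by treatment group, change-from-baseline statistics for every test in its Table 4 and a table of marked abnormalities. The blood-pressure and heart-rate criteria are:

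- Two-way lines: "Increase/decrease in SBP of ≥ 20 (mmHg) versus baseline", the same form for diastolic pressure at 10 mmHg, and "Increase/Decrease in Heart Rate by 15 bpm". The heart-rate line names no reference value.
- Decrease-only lines: "Decrease in systolic blood pressure (SBP) of ≥ 25 (mmHg) versus baseline (orthostatic hypotension", and a diastolic counterpart at 15 mmHg.

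SAP 9.2 fixes the reference: "Baseline is defined as the last available value prior to the subject receiving first dose of study drug infusion (i.e., Day 1". All four blood-pressure lines are measured against it.

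Both schedules of activities (Protocol 1.3, Tables 1 and 2) take vital signs before dosing and 2 and 6 hours after the end of infusion on Days 1, 8, 15, 22 and 29. A same-day pre-dose reading therefore exists at every infusion, but no criterion in SAP 12.4 uses it. Protocol 2.3.1 names falls in blood pressure among the general risks of monoclonal antibodies. Protocol 9.4.2.1 (Part 1) asks for clinically significant vital-sign changes to be summarized but sets no numerical thresholds.

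**The concern.** The protocol itself names a fall in pressure after infusion as a risk, and the reading schedule can show one. The planned criteria are not well matched to it, for two reasons.

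First, a line that counts a change in either direction is a poor detector of a shift in one direction. A drug that lowers pressure moves some patients into the line through falls and others out of it through fewer rises.

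Second, from infusion 2 onward each post-infusion reading is compared with a value taken one to four weeks earlier. Week-to-week variation is added to the change, while the quantity of interest is the change within the day.

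What is at stake is the sensitivity of a pre-specified safety display to a modest acute fall at infusions 2 to 5. The efficacy result and dose-escalation decisions are not affected.

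**Working it through.** **No figure to reproduce.** The documents state no SD, correlation, sample size or power for vital signs. What follows is illustrative. The one document input is 58 patients per arm in Part 2 (SAP 6.1.1); everything else is an assumption, shown over a range.

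**Model.** Systolic pressure has total SD *s*, within-day correlation *w* and across-week correlation *a*. The variance components are person *a·s²*, day *(w − a)·s²* and reading *(1 − w)·s²*. The drug lowers pressure by 5 or 10 mmHg at 2 h and 6 h of infusions 2 to 5. A patient counts if any of those 8 readings meets the row. Rates come from 400,000 simulated patients per arm. Power is the exact binomial power of a two-sided 5% pooled two-proportion test with 58 per arm; repeat runs move it by about one percentage point.

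**Why the reference matters.** The SD of one change is *s*·√(2(1 − ρ)), with ρ = *a* against Day 1 and ρ = *w* against same-day pre-dose. At *s* = 15, *w* = 0.8, *a* = 0.6:

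- Day 1: 15 × √0.8 = 13.4 mmHg
- Same day: 15 × √0.4 = 9.5 mmHg

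Multiplying by √(2/58) gives the SE of the arm difference in mean change: 2.49 and 1.76 mmHg. A 5 mmHg fall is then 5/2.49 = 2.0 SE against Day 1 and 5/1.76 = 2.8 SE against same-day pre-dose. Over all settings the ranges are 1.7 to 2.5 and 2.3 to 3.5 SE, and the two are equal when *w* = *a*.

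**Why the two-way line is weak.** In the same setting with a 5 mmHg fall, patients with a fall of 20 mmHg or more against Day 1 go from 26% on placebo to 42% on active (+16). Patients with a rise of 20 mmHg or more go from 26% to 14% (−12). The combined line moves by about 16 − 12 = 4 points. Over the six settings it moves 2 to 7 points, with 6-13% power.

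**True 5 mmHg fall: % of patients active/placebo, then power**

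| SD, *w*/*a* | Planned fall ≥ 25, Day 1 | Falls-only ≥ 20, Day 1 | Falls-only ≥ 20, same day |
|---|---|---|---|
| 15, 0.8/0.6 | 26.0/14.0, 38% | 41.9/26.0, 44% | 34.1/12.3, 82% |
| 15, 0.7/0.6 | 27.1/14.6, 39% | 43.4/27.0, 45% | 51.3/26.9, 77% |
| 15, 0.8/0.5 | 31.7/19.3, 34% | 46.6/31.6, 37% | 34.1/12.3, 82% |
| 15, 0.7/0.7 | 19.3/8.4, 40% | 36.3/19.3, 54% | 51.3/26.9, 77% |
| 12, 0.8/0.6 | 14.0/5.2, 37% | 29.7/14.0, 55% | 16.4/3.2, 71% |
| 18, 0.8/0.6 | 36.3/23.7, 32% | 50.6/36.3, 34% | 49.6/25.2, 78% |

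At SD 12 the same-day row has a smaller gap than the Day 1 row (13 against 16 points), but its placebo rate is 3% instead of 14%, so it still discriminates better.

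**True 10 mmHg fall: gap between arms over the six settings**

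- Planned 25 mmHg decrease row: 24 to 29 points, 86-97% power
- Two-way 20 mmHg line: 7 to 24 points
- Falls-only 20 mmHg against Day 1: 29 to 37 points
- Falls-only 20 mmHg against same-day pre-dose: 47 to 54 points

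**Same-day reference on the 25 mmHg row.** For a 5 mmHg fall this gives 9-60% power, against 32-40% as planned. It is not a consistent gain.

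**Second variance model.** This one counts all 17 scheduled post-baseline readings: 2 on Day 1, 4 × 3 on Days 8 to 29, and 3 at follow-up. Between-day/within-day SDs are 6/5, 8/6 and 10/7 mmHg, and the fall is 8 mmHg after every infusion. The two-way 20 mmHg line moves 18, 11 and 5 points, and the 25 mmHg decrease row about 16 to 17. A same-day falls-only 20 mmHg count on the 10 post-infusion readings moves 32, 43 and 46. The pattern is the same.

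**The case against.** The strongest reply is that falls already have their own rows. This stands: the 25/15 mmHg rows are adequate for a fall of about 10 mmHg when the 8 post-infusion readings are counted. If all 17 post-baseline readings count and the effect also occurs on Day 1, power for 10 mmHg drops to 72-92%, which is still useful. It also follows that splitting the 20 mmHg line adds little by itself. For a 5 mmHg fall it gains 2 to 6 points of power over the planned row in four of six settings. The consistent gain comes from combining a falls-only 20 mmHg row with the same-day reference.

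A second reply is that mean same-day change is already obtainable. If change from baseline is tabulated by time point and data are complete, the 2 h mean minus the same day's pre-dose mean equals the mean same-day change, because the Day 1 value cancels. This stands for the mean. Subtraction gives neither the SD of that change nor a count of patients. At infusion 1 the SAP baseline is normally the same-day pre-dose reading anyway.

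Third, the list of criteria is open and SAP 9.1 leaves layout to mock shells, so increases and decreases may yet be shown separately. That is possible, but the SAP text does not commit to it. For heart rate, the ECG section already has a rise-only criterion: at least 30% above baseline "AND observed heart rate > 90 (bpm".

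A reader might also infer that measured fever goes uncounted, since no temperature threshold is given. The documents do not support that as a defect. The protocol asks that vital signs, "and oral temperature) will be summarized by assessment day showing absolute values, change from baseline values, and clinically significant changes", be summarized, but sets no temperature cut-off. Temperature is in SAP Table 4, so it has by-arm change statistics and a listing. Abnormal vital signs, "including those that worsen from baseline, considered clinically significant" by the investigator, are AEs and are tabulated as "AEs by system organ class (SOC) and preferred term (PT". Only fever that was not judged significant or not reported remains outside the by-arm counts.

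**Conclusion.** The point holds as an optional improvement. As worded, the 20/10 mmHg and 15 bpm lines combine opposite movements, every blood-pressure criterion uses the Day 1 baseline, and the same-day pre-dose readings are unused in the criteria. A fall of about 10 mmHg should still show in the planned 25 mmHg row. A 5 mmHg acute fall at infusions 2 to 5 probably would not: roughly 32-40% power, against 71-82% for a same-day falls-only 20 mmHg row. These figures rest on assumed systolic SDs of 12 to 18 mmHg, correlations of 0.7 to 0.8 within day and 0.5 to 0.7 across weeks, and 58 per arm, with power as a yardstick for a descriptive table.

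Two stronger readings do not follow. The comparison between arms is not biased, because both arms are counted by the same rules. The SAP does not leave falls in pressure uncounted, because the 25/15 mmHg rows count them and the by-patient listings hold every reading. No decision rule depends on these tables. What would be missing is a sensitive display fixed in advance.

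**What to change.** In SAP 12.4:

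1. Keep the Day 1 baseline and the 25/15 mmHg decrease rows unchanged.
2. Show decreases and increases as separate rows at 20/10 mmHg and 15 bpm, and state baseline as the heart-rate reference.
3. For each dosing day, tabulate by arm the change from same-day pre-dose to 2 h and 6 h, with a falls-only count at 20 mmHg systolic and 10 mmHg diastolic on that change.

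A by-arm count of measured fever could be added as an extra, but the point does not depend on it.

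The cost is a few lines of SAP wording and slightly longer descriptive tables. All the readings are already scheduled, so no new data are needed.
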